7.3. Relationship to Study Drug

Investigators should use their knowledge of the subject, the information from the patients health care providers and the circumstances surrounding the event, and an evaluation of any potential alternative causes to determine whether or not an AE is considered to be related to study drug, indicating on the eCRF that an AE is either related or unrelated. The following guidance should be taken into consideration when determining the relationship of an AE to study drug:

- Temporal relationship of event onset to initiation of study drug
- Course of the event, considering especially the effects of dose reduction, discontinuation of study drug, or reintroduction of study drug (where applicable)
- Known association of the event with study drug or with similar treatments
- Known association of the event with the disease under study
- Presence of risk factors in the subject or environment, or use of concomitant medications known to be associated with the event
- Presence of treatment-unrelated factors that are known to be associated with the occurrence of the event
- Whether there is a reasonable alternative explanation for the event

All AEs (including SAEs) will be assessed for the relationship of the AE to the study drug using the following definitions: not related; unlikely; possibly; probably; or definitely. For reporting and data analysis purposes, AEs reported with a causality assessment of “Definitely”, “Probably”, and “Possibly” are to be considered as “having a reasonable causal relationship” to study drug.

7.4 Study Monitoring

7.4.1 Adverse Events

The study coordinator and medical monitor will review and assess EA reports for potential impact on the study participant safety and protocol conduct. The XFBD001 protocol chairs will review all serious adverse events, and this review will be conducted on a weekly basis in a blinded fashion.

8 TOXICITY MANAGEMENT

8.1 Toxicity Grading

Criteria for participant management, dose interruptions, dose adjustments and discontinuation, or changes in treatment will be described only for toxicities attributable to the XFBD. The grading system for toxicities is CTCAE version 5.

https://ctep.cancer.gov/protocoldevelopment/electronic_applications/docs/CTCAE_v5_Quick_Reference_8.5x11.pdf

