4.2 Inclusion Criteria

- 4.2.1 Participant provides informed consent prior to initiation of any study procedures.
- 4.2.2 Individual 18 to 75 years of age.
- 4.2.3 Documentation of confirmed active SARS-CoV-2 infection, as determined by an FDA authorized molecular test conducted at any US clinic or laboratory that has a Clinical Laboratory Improvement Amendments (CLIA) certification or its equivalent from any respiratory specimen collected <96 hours prior to study entry.
- 4.2.4 Mild or Moderate COVID-19 experiencing at least one SARS-CoV-2 infection symptom including:

Mild Covid-19

- Symptoms of mild illness with COVID-19 that could include fever, cough, sore throat, malaise, headache, muscle pain, gastrointestinal symptoms, without shortness of breath or dyspnea

Moderate Covid-19

- Symptoms of moderate illness with COVID-19, which could include any symptom of mild illness or shortness of breath with exertion
- Presence of clinical signs consistent with moderate illness with COVID-19, such as respiratory rate \geq 20 breaths per minute, saturation of oxygen (SpO2) $>$ 93% on room air at sea level, heart rate \geq 90 beats per minute from a health care encounter within 48 hours.

- 4.2.5 Agrees to not participate in another clinical trial for the treatment of COVID-19 or SARS-CoV-2 during the study period up until reaching hospitalization or 28 days, whichever is earliest.
- 4.2.6 Agrees to not utilize TCM outside of this study.
- 4.2.7 Willing to be randomized to XFBD and placebo control arm for 14 days, and followed up to 12 weeks.
- 4.2.8 Willing to comply with the study related questionnaires, procedures and measurements.
- 4.2.9 Will to not become pregnant during the 14 days of test substance ingestion using appropriate accepted methods of contraception. Acceptable methods of contraception include: postmenopausal 1 year of amenorrhea and over 50 years of age; prior tubal ligation or hysterectomy; or barrier contraception using condom or diaphragm plus spermicide.
- 4.2.10 Able to provide the identity of their health care provider or health system clinical care entry information.
- 4.2.11 Able to utilize telephone and telehealth platform to comply with the study related questionnaires, procedures and measurements. Established during the recruitment process.
- 4.2.12 Able to speak and communicate in English, Spanish, Mandarin Chinese or Cantonese.

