8.3 Management of Side Effects

It is possible that some participants will experience transient or prolonged AEs during the study. However, it is important to note that, in this trial, the visits will be conducted remotely and hence, AEs will be assessed remotely.

Management of AEs and side effects will be by the participant's health care providers. The single exception is to stop the study medication or placebo in the event of greater than grade 1 AE. Clear instructions to participants to call 911, go to their local urgent care or emergency care center, or contact their health care provider are provided during the enrollment, consent process and by the app participants use to report symptoms.

Patients report symptoms (PRO) that include potential adverse events daily and weekly on the app. In the event, they have symptoms necessitating an encounter with the health provider, contact between the health provider by the study coordinator will be made. Participants will be given a card indicating they are on the trial and the telephone number for the study team. Participants are instructed to notify the study coordinator when they seek a health encounter. A copy of the medical records related to that encounter are to be obtained to collect additional data to appropriately grade any potential toxicity.

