8.3.3 Nervous and Psychiatric Events

Headache, psychosis, insomnia, heatstroke, nervousness, anxiety, strokes, seizures, coma; are listed as potential side effects of the components of XFBD.

Table 8.3.3 – Selected Nervous System and Psychiatric Adverse Event Grading (CTCAE)

Grade	1	2	3	4	5
Anxiety	Mild symptoms; intervention not indicated	Moderate symptoms; limiting instrumental ADL	Severe symptoms; limiting self-care ADL; hospitalization indicated	Life-threatening consequences; urgent intervention indicated	
Depressed levels of consciousness	Decreased level of alertness	Sedation; slow response to stimuli; limiting instrumental ADL	Difficult to arouse	Life-threatening consequences; coma; urgent intervention indicated	
Headache	Mild pain	Moderate pain; limiting instrumental ADL	Severe pain; limiting self-care ADL		
Insomnia	Mild difficulty falling asleep, staying asleep or waking up early	Moderate difficulty falling asleep, staying asleep or waking up early	Severe difficulty falling asleep, staying asleep or waking up early		
Psychosis	Mild psychotic symptoms	Moderate psychotic symptoms (disorganized speech;	Severe psychotic symptoms (paranoid, extreme	Life-threatening consequences; threats of harm to self or others;	Death

		impaired reality testing)	disorganization) hospitalization not indicated; new onset	hospitalization indicated	
Stroke	Incidental radiographic findings only	Mild to moderate neurologic deficit; limiting instrumental ADL	Severe neurologic deficit; limiting care ADL; hospitalization	Life-threatening consequences; coma; urgent intervention indicated	Death
Seizure	Brief partial seizure and no loss of consciousness	Brief generalized seizure	New onset seizures (partial or generalized); multiple seizures despite medical intervention	Life-threatening consequences; prolonged repetitive seizures	Death

Grade 1 Anxiety and insomnia do not require treatment discontinuation. For grade 2 anxiety or insomnia the study agent is discontinued. For all other grade 1 or greater events in table 8.3.3 participants are instructed to discontinue study medication or placebo and must be referred to their health care provider for management.

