9 CRITERIA FOR DISCONTINUATION

9.1 Permanent and Premature Treatment Discontinuation

- Drug-related toxicity or allergic reaction (see [section 8.0](#)).
- Requirement for prohibited concomitant medications (see [section 5.4.1](#)).
- Request by participant to terminate treatment.
NOTE: The reason for treatment discontinuation should be documented (e.g. concern for AE, lack of efficacy, or other reason).
- Clinical reasons believed life threatening by the physician, even if not addressed in the [section 8.0](#) of the protocol.

9.2 *Premature Study Discontinuation*

- 9.2.1 Failure to take the first dose (directly observed/confirmed over telephone) of study treatment within 2 days of study entry.
- 9.2.2 Request by the participant to withdraw consent.
- 9.2.3 Request of the health care provider if she or he thinks the study is no longer in the best interest of the participant.
- 9.2.4 At the discretion of the IRB/EC, FDA, NIAID, Office for Human Research Protections (OHRP), other government agencies as part of their duties, investigator, or industry supporter.

In the event that a participant prematurely discontinues from the study, unless they have withdrawn consent, sites will attempt to obtain information regarding vital status (including date last seen alive, hospitalization, date of death, and primary cause of death) from other sources (such as family members, other designated contacts, or clinic records) per [section 6.2.15](#).

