10.2.2 Secondary Outcome Measures

- 10.2.2.1 To document the effect of XFBD on Symptom Severity Score within 28 days of

study entry.

- 10.2.2.2 To document the proportion of patients who are compliant taking greater than 90% of the test substance as measured by self-report
- 10.2.2.3 To document the proportion of patients who comply with symptom monitoring.
- 10.2.2.4 To document the proportion of patients who comply with repeated clinical testing.
- 10.2.2.5 To document cumulative incidence of serious adverse events, and adverse events leading to early discontinuation of XFBD or placebo.
- 10.2.2.6 To document cumulative incidence of grade 3 and 4 adverse events.
- 10.2.2.7 To obtain levels (detectable versus not detectable, and continuous on log10 scale) of SARS-CoV-2 RNA from nasal swabs at approximately days 1, 7 and 14 among a subset.

10.3 *Randomization and Stratification*

[figure not shown]
Eligible participants will be randomized using a 1:1 ratio to each of the study arms. Housemates of participants previously enrolled will be independently randomized so that housemates will not be clustered within treatment group.

Randomization will be stratified by “high” vs “low” risk of severe disease, where “high” risk is defined by any of the following: age ≥ 60 years, or having any of a number of conditions, as described in section 3.3.

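### Sections 8.1 and 9.1 tie toxicity stops to attribution to XFBD, but 8.3 and 8.3.3 stop the agent with no such condition, which blurs the compliance and discontinuation outcomes

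*Combined protocol and SAP*

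**What the plan says.** **Where attribution is required.** Section 8.1 (Toxicity Grading) states that criteria for "discontinuation, or changes in treatment will be described only for toxicities attributable to the XFBD". Section 9.1 gives "Drug-related toxicity or allergic reaction" as its toxicity ground for stopping treatment and refers back to section 8. It also lists grounds that need no attribution, among them "Request by participant to terminate treatment".

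**Where it is not stated.** Section 8.3 leaves management to the participant's own providers, with one carve-out: "The single exception is to stop the study medication or placebo in the event of greater than grade 1 AE". Section 8.3.3 opens with an exemption, "Grade 1 Anxiety and insomnia do not require treatment discontinuation", and then says: "For all other grade 1 or greater events in table 8.3.3 participants are instructed to discontinue study medication or placebo". Headache is in that table, and its grade 1 is mild pain.

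**Entry symptoms.** Section 4.2 (item 4.2.4) describes mild disease as "Symptoms of mild illness with COVID-19 that could include fever, cough, sore throat, malaise, headache, muscle pain, gastrointestinal symptoms".

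**What an adverse event is.** Section 7.1 includes events whatever their cause, provided that they are new or worse than at baseline, and excludes worsening of COVID-19. Section 7.3 asks for a causality assessment of every adverse event.

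**Outcomes that depend on stops.** Secondary outcome 10.2.2.2 is "To document the proportion of patients who are compliant taking greater than 90% of the test substance as measured by self-report". Secondary outcome 10.2.2.5 includes adverse events that lead to early discontinuation. Neither says how a stop required by the protocol is handled.

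**The concern.** Treatment must begin within 96 hours of symptom onset, so the 14 dosing days overlap the acute illness. Some events that trigger a stop are also symptoms of that illness, headache being the clearest case. If the stop depends on attribution, a headache judged to be COVID-19 does not end treatment. If it does not, the same headache ends it.

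Exposure, the compliance proportion and the count of discontinuations for adverse events would then depend partly on which section the staff followed. This is a feasibility pilot, and compliance and tolerability are among the quantities it is meant to hand to the next trial. A compliance figure that mixes missed doses with doses withheld on instruction is hard to use for that purpose.

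**Working it through.** The documents state no derived figure on this point, so there is none to reproduce. The check compares the text and then does simple dose arithmetic.

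**Step 1: the rules applied to two participants.** The differing grade thresholds in 8.3 and its subsections are a separate matter and are set aside here.

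| Participant | 8.3.3 taken literally | 8.1 and the toxicity item of 9.1 | 7.1 |
|---|---|---|---|
| Enrolled with cough; new mild headache on Day 3 | Stop | Stop only if attributed to XFBD | Adverse event if new and not COVID-19 worsening; otherwise not |
| Enrolled with mild headache, unchanged on Day 3 | Stop, since no exemption is stated | Stop only if attributed to XFBD | Not an adverse event |

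For each participant, the outcome depends on which text is followed.

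**Step 2: does 7.3 settle it?** Section 7.3 asks for a related or unrelated entry and also for a five-level scale. It groups possible, probable and definite for reporting and analysis. It does not say which category triggers a stop. Its guidance weighs known association with the study drug and known association with the disease. Headache has both: Table 8.2 lists it for components of XFBD, and 4.2.4 lists it for COVID-19.

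**Step 3: the compliance threshold.** Planned doses: 2 per day × 14 days = 28 (section 5.1). More than 90% means more than 0.90 × 28 = 25.2 doses.

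- 25/28 = 89.3%, which fails.
- 26/28 = 92.9%, which passes.

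At least 26 doses are needed, and dose 26 is the second dose of Day 13. Anyone told to stop before it fails 10.2.2.2. A participant stopped on Day 3 has taken at most 2 × 3 = 6 doses, and 6/28 = 21.4%, although 6 of 6 doses due were taken.

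**Step 4: where such a stop is counted.**

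| Classification of the event under 7.1 | 10.2.2.2 | 10.2.2.5 |
|---|---|---|
| Adverse event | Fails | Counted |
| Worsening of COVID-19 | Fails | Not counted |

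**Step 5: size.** The documents give no rate for new or worse headache during treatment. With an assumed 5% to 20% of the 60 participants stopped in this way:

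- 0.05 × 60 = 3, and 0.20 × 60 = 12.
- If all were stopped before dose 26, the highest attainable compliance would be 57/60 = 95% down to 48/60 = 80%.

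Section 2.1 reports headache or dizziness in 12.1% of patients (0.121 × 60 = 7.3). That figure cannot be used as the rate here. It pools two symptoms, of which dizziness stops treatment only from grade 2 under 8.3.2, and it includes symptoms present at diagnosis.

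**The case against.** The best defence is that 8.1 is a scope sentence for the whole of section 8. On that reading, everything in 8.3 to 8.3.4 already concerns XFBD side effects, 7.3 supplies the causality judgement, and the subsections simply do not repeat the condition. The title of Table 8.3.3 also refers to adverse events, which would bring in 7.1's test of new or worse than baseline and so protect an unchanged entry headache. The medical monitor determines clinical significance, and only one initial site is named, so practice might be fairly uniform. The comparisons are for planning only, in a pilot that is not powered for them.

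Much of this is fair, and it narrows the point. It does not remove it. The instruction in 8.3.3 is unconditional as written. Even if 8.1 governs, no section says which causality category leads to a stop. Even if 7.1 governs, a new headache in a patient with COVID-19 can be classed either way. The compliance outcome is affected whichever class is chosen, once the agent has been stopped.

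Stronger readings are tempting but not supported:

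- **That 9.1 allows stops only for drug-related toxicity.** It also lists participant request, prohibited medication and life-threatening clinical reasons.
- **That every listed event stops treatment.** Their own subsections do not require a stop for grade 1 gastrointestinal or cardiovascular events, grade 1 anxiety or insomnia, grade 2 nausea, or grade 1 or 2 fatigue.
- **That disease symptoms necessarily count as intolerance.** That depends on the classification under 7.1.
- **That the arms would be affected unequally.** This is possible if one arm is more symptomatic, but nothing in the documents establishes it.

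**Conclusion.** The point holds in a limited form. Section 8.1 and the toxicity item of 9.1 require attribution to XFBD; 8.3 and 8.3.3 state stops without it; and 8.3.3 is silent on symptoms present at entry or due to COVID-19. Two careful readers could treat the same participant differently.

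One consequence is certain: a required stop before dose 26 of 28 is scored as non-compliance whatever the participant's adherence. The other is conditional: it enters 10.2.2.5 only if the event is classed as an adverse event.

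The size is not known. The range of 3 to 12 of 60, and the matching compliance ceiling of 95% to 80%, rest on an assumed rate and on every such participant being stopped before dose 26. They are illustrations and should not be read as forecasts. The matter should be corrected because it affects what the pilot's compliance and discontinuation figures mean. It does not undermine the design.

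**What to change.** 1. The sponsor reconciles 7.1, 7.3, 8.1, 8.3 to 8.3.4 and 9.1 so that one stated attribution condition and one baseline reference apply to the stops. Which clinical rule should apply is for the sponsor to decide; none is proposed here.
2. Report 10.2.2.5 split by the 7.3 causality category, and list separately the stops for symptoms classed as COVID-19.
3. Keep 10.2.2.2 as doses taken divided by 28, and add doses taken divided by doses due before a protocol-required stop, hospitalization or death.

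The cost is protocol wording and one extra summary table. Sections 6.2.23 and 9.1 already ask for the reason for discontinuation, and 7.3 already asks for causality on adverse events, so little new data collection is needed.

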8.2 Potential Toxicities

The side effects which are described with the components of the XFBD are listed in Table 8.2.

Table 8.2 Side Effects of the Components of XFBD

Medicinal	Latin	Potential Side Effects	Allergic Reactions
麻黃	Ephedrae Herba	tachycardia, palpitations, increased blood pressure, nausea, vomiting, dizziness, strokes, seizures, sudden death, psychosis, insomnia, heatstroke, nervousness, anxiety, sweating avoid taking with MAO inhibitors	To any ephedra plant (i.e. Mormon Tea)
苦杏仁	Armeniacae Semen Amarum	dizziness, sudden fainting, palpitations, headache, nausea, vomiting, seizures, coma, cyanosis	To almonds or any component of almonds
生石膏	Gypsum Fibrosum	upset stomach, loss of appetite	To calcium sulfate, calcium or sulfates
薏苡仁	Coicis Semen	upset stomach, frequent urination, excessive sweating Use with Caution: Pregnancy	To coix seed, also known as Job's tears
苍术	Atractylodis Rhizoma	nausea, dry mouth, bad taste in mouth, upset stomach, increased gastrointestinal motility	To any plant in the genus Atractylodes , such as ragweed
广藿香	Pogostemonis Herba	nausea, upset stomach, increased gastrointestinal motility	To any plant in the Pogostemon genus (i.e. Patchouli)
青蒿	Artemisiae Annuae Herba	nausea, vomiting, upset stomach, decreased blood pressure, decreased heart rate, decreased blood sugar, increased CYP3A4 and 2B6 activity	To any Artemisiae or mugwort plant
马鞭草	Verbenae Herba	nausea, vomiting, dizziness, headache, abdominal pain Contraindicate for pregnant patients	To any Verbena plants, also known as verbena or vervain
虎杖	Polygoni Cuspidati Rhizoma et Radix	nausea, vomiting, stomach upset, abdominal pain, diarrhea, dehydration; large doses can cause liver damage and could result in leukopenia and hematuria Contraindicate for pregnant patients	To Polygonum cuspidatum , also known as Japanese Knotweed, Japanese Fleeceflower
芦根	Phragmitis Rhizoma	fatigue, loss of appetite, diarrhea	To any Phragmites , also known as common reed

葶苈子	Descurainiae Semen	nausea, vomiting, stomach upset	To Descuriania sophia also known as flixweed or tansy mustard To similar plants such as garden cress, maca or dittany
化橘红	Citri Grandis Exocarpium	large doses can lead to sore or dry throat	To the pomelo fruit or peel; citrus fruits
甘草	Glycyrrhizae Radix et Rhizoma	large doses can lead to fatigue, muscle weakness, increased blood pressure, headache, stomach upset, reduced testosterone levels; long term use can lead to abnormal weight gain	To any Glycyrrhiza plant also known as licorice root

8.3 Management of Side Effects

It is possible that some participants will experience transient or prolonged AEs during the study. However, it is important to note that, in this trial, the visits will be conducted remotely and hence, AEs will be assessed remotely.

Management of AEs and side effects will be by the participant's health care providers. The single exception is to stop the study medication or placebo in the event of greater than grade 1 AE. Clear instructions to participants to call 911, go to their local urgent care or emergency care center, or contact their health care provider are provided during the enrollment, consent process and by the app participants use to report symptoms.

Patients report symptoms (PRO) that include potential adverse events daily and weekly on the app. In the event, they have symptoms necessitating an encounter with the health provider, contact between the health provider by the study coordinator will be made. Participants will be given a card indicating they are on the trial and the telephone number for the study team. Participants are instructed to notify the study coordinator when they seek a health encounter. A copy of the medical records related to that encounter are to be obtained to collect additional data to appropriately grade any potential toxicity.

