8.3.1 Gastrointestinal Effects

Sore or dry mouth or throat, bad taste in mouth, loss of appetite, upset stomach, nausea, vomiting increased gastrointestinal motility, abdominal pain, diarrhea, are listed as potential side effects of the components of XFBD.

Symptom of loss of appetite (anorexia) is coded as a grade of nausea for the purposes of this trial.

Table 8.3.1 – Selected Gastrointestinal Adverse Event Grading (CTCAE)

Grade	1	2	3	4	5
Abdominal pain	Mild pain	Moderate pain; limiting instrumental ADL	Severe pain; limiting self care ADL		
Nausea	Loss of appetite without alteration in eating habits	Oral intake decreased without significant weight loss, dehydration or malnutrition	Inadequate oral caloric or fluid intake; tube feeding, TPN, or hospitalization indicated		
Diarrhea	Increase of <4 stools per day over baseline;	Increase of 4 - 6 stools per day over baseline;	Increase of ≥ 7 stools per day over baseline;	Life-threatening consequences;	Death

	mild increase in ostomy output compared to baseline	moderate increase in ostomy output compared to baseline; limiting instrumental ADL	hospitalization indicated; severe increase in ostomy output compared to baseline; limiting self-care ADL	urgent intervention indicated	
Vomiting	Intervention not indicated	Outpatient IV hydration; medical intervention indicated	Tube feeding, TPN, or hospitalization indicated	Life-threatening consequences	Death

Grade 1 abdominal pain, nausea, diarrhea and vomiting do not require treatment discontinuation. In the event of GI symptoms, the study staff should review with the participant if XFBD is being taken with food. For grade 1 side effects, participants may be referred to their primary health care providers. For grade 2 nausea the study agent may be continued. For all other grade 2 or greater events or grade 3 nausea participants are instructed to discontinue study medication or placebo and must be referred to their health care provider for management.

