8.3.4 Other side effects

Fatigue, excessive sweating, muscle weakness, weight gain, dehydration, liver damage, reduced testosterone levels, sudden death, blood in the urine, frequent urination, or low white blood cell count.

Table 8.3.4 – Selected Other Adverse Event Grading (CTCAE)

Grade	1	2	3	4	5
Fatigue	Fatigue relieved by rest	Fatigue not relieved by rest; limiting instrumental ADL	Fatigue not relieved by rest, limiting self-care ADL		
Urinary frequency	Present	Limiting instrumental ADL, medical management indicated			
Dehydration	Increased oral fluids indicated; dry mucous membranes; diminished skin turgor	IV fluids indicated	Hospitalization indicated	Life-threatening consequences; urgent intervention indicated	Death
Hypoglycemia	<LLN - 55 mg/dL; <LLN - 3.0 mmol/L	<55 – 40 mg/dL; <3.0 - 2.2 mmol/L	<40 - 30 mg/dL; <2.2 - 1.7 mmol/L	<30 mg/dL; <1.7 mmol/L; life threatening consequences;	Death

				seizures	
White blood cell decreased	<LLN - 3000/mm3; <LLN - 3.0 x 10e9 /L	<3000 - 2000/mm3; <3.0 - 2.0 x 10e9 /L	<2000 - 1000/mm3; <2.0 - 1.0 x 10e9 /L	<1000/mm3; <1.0 x 10e9 /L	
Testosterone deficiency	Asymptomatic; mild symptoms with no intervention indicated	Replacement therapy initiated			
Hepatic failure			Asterixis; mild encephalopathy; drug-induced liver injury (DILI); limiting self-care ADL	Life-threatening consequences; moderate to severe encephalopathy; coma	Death
Hematuria	Asymptomatic; clinical or diagnostic observations only; intervention not indicated	Symptomatic; urinary catheter or bladder irrigation indicated; limiting instrumental ADL	Gross hematuria; transfusion, IV medications, or hospitalization indicated; elective invasive intervention indicated; limiting self-care ADL	Life-threatening consequences; urgent invasive intervention indicated	Death

In the event of grade 1 or 2 fatigue the study agent may be continued, the study participant may contact their primary health care provider. The study agent should be discontinued, and the patient referred to their primary health care providers for grade 3 fatigue.

In the event of all other grade 1 or greater other side effects in table 8.3.4 the study staff must refer the participant to their primary health care providers and discontinue study agent.

Dehydration, hypoglycemia, white blood cell decreased, testosterone deficiency, hepatic failure (measure of hepatic damage) and hematuria are captured on review of medical records for participants who have a health care encounter.

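### Section 8.3 stops study agent above grade 1, yet 8.3.1 and 8.3.4 allow it to continue at grade 2 nausea and grade 2 fatigue, and no text says which prevails

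*Combined protocol and SAP*

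**What the plan says.** Section 8.3 notes that visits, and therefore AE assessments, are remote. It assigns management of side effects to the participant's providers and then states: "The single exception is to stop the study medication or placebo in the event of greater than grade 1 AE". The sentence is not limited by event type.

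The subsections set rules by event:

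- **8.3.1, gastrointestinal.** "For grade 2 nausea the study agent may be continued". Then: "For all other grade 2 or greater events or grade 3 nausea participants are instructed to discontinue study medication or placebo".
- **8.3.2, cardiovascular.** Study agent is discontinued at grade 2 or above.
- **8.3.3, nervous and psychiatric.** Grade 1 anxiety and insomnia do not require a stop; grade 2 does. For the rest: "For all other grade 1 or greater events in table 8.3.3 participants are instructed to discontinue study medication or placebo".
- **8.3.4, other.** "In the event of grade 1 or 2 fatigue the study agent may be continued", with a stop at grade 3 fatigue. For all other events at grade 1 or above "in table 8.3.4 the study staff must refer the participant to their primary health care providers and discontinue study agent".

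Section 8.1 limits the management criteria to toxicities attributable to XFBD. Section 9.1 lists drug-related toxicity as a reason to stop treatment and points to section 8 as a whole. Neither ranks the general sentence in 8.3 against the event rules.

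**The concern.** A study coordinator who hears by telephone or app of grade 2 nausea or grade 2 fatigue finds one sentence that says stop and another that allows treatment to go on. Staff who read the section differently would manage like cases differently. The trial assesses AEs remotely and has no separate monitoring committee (10.5), so staff depend heavily on the written rule.

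The affected events are not remote possibilities for this product. Table 8.2 lists nausea for 8 of the 13 components. Section 8.3.1 also codes loss of appetite as nausea, which brings in two more (gypsum and phragmites), for 10 of 13. Fatigue is listed for 2 of 13.

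The statistical consequence is narrow. AEs that lead to early discontinuation are part of a secondary outcome (1.3.6 and 10.2.2.5). Grade 2 events must be recorded under 7.2 whichever text is followed, so the AE listing itself does not depend on the choice. What can change is whether such an event is also counted as one that ended treatment.

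**Working it through.** The plan gives no figure to reproduce. The check compares the rules and counts table rows.

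**Step 1: rows.** Table 8.3.1 has 4 events, Table 8.3.2 has 7, Table 8.3.3 has 7 and Table 8.3.4 has 8: 4 + 7 + 7 + 8 = 26.

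**Step 2: opposite actions at the same grade.**

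| Event and grade | General sentence in 8.3 | Event rule |
|---|---|---|
| Nausea, grade 2 | stop | may continue (8.3.1) |
| Fatigue, grade 2 | stop | may continue (8.3.4) |

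That is 2 of 26 events, each at one grade. At grade 3 both texts stop study agent for both events.

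**Step 3: event rules that stop earlier than 8.3.**

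- Table 8.3.3, leaving out anxiety and insomnia: depressed consciousness, headache, psychosis, stroke, seizure = 5, all with a grade 1 definition.
- Table 8.3.4, leaving out fatigue: urinary frequency, dehydration, hypoglycemia, white blood cell decrease, testosterone deficiency, hematuria = 6 with a grade 1 definition.
- Total: 5 + 6 = 11. Hepatic failure also falls under the 8.3.4 rule and would make 12 by row, but its grade 1 and 2 cells are empty, so no grade 1 stop can arise.

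In these 11 cases 8.3 does not tell staff to continue at grade 1. Someone who stops at grade 1 complies with both texts. The tension is only with the word *single* in 8.3.

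**Step 4: rows that agree with 8.3 on stopping.** 26 − 2 − 11 = 13: three in Table 8.3.1, all seven in Table 8.3.2, two in Table 8.3.3 (anxiety, insomnia) and one in Table 8.3.4 (hepatic failure).

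**Step 5: search for a tie-breaker.** Section 8.1 restricts by attribution, which is a different question from precedence. Section 9.1 refers back to section 8 without distinguishing its parts. No other supplied text settles it.

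**The case against.** The strongest reply is that specific text overrides general text. Sections 8.3.1 to 8.3.4 sit under 8.3, and the wording of 8.3.1 ("For all other grade 2 or greater events or grade 3 nausea participants are instructed to discontinue study medication or placebo") is plainly a carve-out for grade 2 nausea. Section 8.3.4 separates fatigue from the other events in the same way. On this reading all that is missing is a cross-reference.

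This is plausible and may well be the intent. It does not remove the problem, because 8.3 calls its rule the single exception, which leaves no room for further unstated ones. Nor is the general sentence merely introductory: 8.3.4 names excessive sweating and muscle weakness as side effects but gives them no table row, so 8.3 supplies the only grade threshold for them.

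A second reply is that some grade 2 nausea or fatigue will never reach the rule. Section 7.1 excludes worsening of COVID-19 from AEs and gives the medical monitor the decision on clinical significance. That stands, but new or worsened events can still qualify.

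Three stronger readings are tempting, and the documents do not support them:

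- **That the 11 grade 1 stops also contradict 8.3.** They do not; an earlier stop breaches no instruction there. Section 7.2 requires recording of AEs of any grade that change treatment, so it allows for stops below grade 2.
- **That the share of table rows measures impact.** Rows are not participants, and no on-treatment event rates are given. Nor can one say how many of the 11 would surface remotely. Five of them (dehydration, hypoglycemia, white blood cell decrease, testosterone deficiency, hematuria) "are captured on review of medical records for participants who have a health care encounter", and grade 1 stroke is defined as "Incidental radiographic findings only". For the remaining five, the app screens in Appendix VI show only part of the symptom list, and none of the five is visible there.
- **That the treatment comparison is compromised.** The trial is double-blind, treatment changes and their reasons are recorded (6.2.23, 9.1), participants who stop treatment stay on study (6.2.17), and 10.6.2 treats comparisons as for planning only.

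**Conclusion.** The inconsistency is real and small in extent. For 2 of 26 tabulated events, nausea and fatigue at grade 2, the general and specific texts give opposite actions, and nothing supplied says which governs. The 11 grade 1 stops are a secondary drafting point: they are compatible with the instruction in 8.3 but not with its description as the only exception.

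The conclusion rests on reading 8.3 as an operative rule, not a loose introduction, and on the supplied text alone. How many participants would be affected is unknown. It should be fixed because it concerns when participants stop treatment and how consistently AEs leading to early discontinuation are counted under 10.2.2.5. It does not threaten any inference that the pilot intends to draw. No view is taken here on which threshold is correct.

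**What to change.** Reconcile 8.3 with 8.3.1, 8.3.3 and 8.3.4 so that each event and grade has exactly one action, or add a sentence to 8.3 stating whether the general rule or the event rules prevail. If the event rules are to prevail, the description of a single exception needs rewording as well, since the grade 1 stops also depart from it. Which action applies at each grade is for the investigators and medical monitor to decide.

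The cost is amendment wording only: no new data collection and no change to the analyses.
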